9.1 ADVERSE EVENTS

The safety of all subjects enrolled in this study will be monitored throughout the study. Safety monitoring will include history and physical examination with vital signs, adverse event reporting, and laboratory evaluations. Adverse events will be collected and recorded for subjects from Randomization through Study Day 91, or until subject discontinuation within this 91-day period.

ELAD is a combination biologic and medical device product that is regulated as a medicinal product in the US and EU where the study is being conducted. However, adverse events need to be assessed and reported following both the drug and medical device regional requirements.

The Investigator is responsible for assessment of all AEs/SAEs for severity and relationship to the assigned treatment. All SAEs must be reported by the Investigator to the VTL Designee within 24 hours of knowledge. The VTL Designee will report SAEs that meet the criteria for expedited reporting (per the [Investigator's Brochure](#)) to the appropriate health authorities in accord with regional requirements. The Investigator must submit these expedited reports to their IRB/EC in accord with local requirements. Further detail is provided below.

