9.4 REPORTING OF SERIOUS ADVERSE EVENTS

All SAEs defined as being reportable adverse events in accord with 21 CFR 312.32 [that also includes the reporting of suspected unexpected serious adverse reactions (SUSARs)], European database of Suspected Unexpected Serious Adverse Reactions (Eudravilgance – Clinical Trial Module), and serious adverse device effects (SADEs) in accord with 21 CFR 812, in addition to

all other local regulations, that occurs in any subjects participating in this clinical trial, must be reported as described below:

As soon as feasible, but at least within 24 hours of knowledge of a new SAE, the Investigator must report the event to the VTL designee. The SAE reporting form should be completed and submitted irrespective of the volume of information available about the event, though the Investigator is expected to provide as much information as possible.

Information to be sent to VTL (or designee) includes, where applicable:

- Pertinent subject medical history
- Concomitant medications
- Physical examination results, vital signs and laboratory reports if available
- Treatment(s) administered
- Outcome of the event

SAEs should be reported from Randomization through the last day of study participation or through Study Day 91.

Follow-up information to serious adverse events must be provided promptly as it becomes known to the Investigator and submitted to the VTL designee.

The approving IRB/EC must be notified by the Investigator of any fatal, life-threatening and/or serious adverse events regardless of cause on a timely basis according to local regulatory requirements. In addition, a written report of all SAEs will be submitted by the Investigator per local IRB/EC requirements. All subjects with serious adverse events should be followed clinically and by the appropriate diagnostic evaluations until the event (1) resolves, (2) an outcome is reached, or (3) the event is otherwise explained or stabilized.

Subjects withdrawn from the study due to an SAE will be followed by the Investigator until the outcome is determined and, when appropriate, additional written reports and documentation will be provided to the VTL designee.

All SAEs that occur after the discontinuation of treatment with the ELAD System, regardless of relatedness to the study treatment, must be reported to the VTL designee if the onset of the SAE occurred from Randomization through the last day of study participation or through Study Day 91.

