All suspected unexpected serious adverse reactions (SUSARs) related (related is defined as possibly related, probably related, and related) to the investigational product which occur during this study are subject to expedited reporting.

All adverse events, regardless of severity, and whether or not related to the study treatment, will be recorded in the appropriate section of the eCRF.

All adverse events beginning after the discontinuation of treatment with the ELAD System, whether serious or non-serious and regardless of relatedness to the study treatment, must be reported to the Sponsor if the onset of the adverse event occurred during the subject's study

participation (from Randomization through the last day of study participation or through Study Day 91).

All serious adverse events that are unexpected (defined as an adverse event not listed in the [Investigator's Brochure](#)) and related (related is defined as possibly related, probably related, and related) to the investigational product that occur from Randomization through the last day of study participation or through Study Day 91 must be reported to the Sponsor in a timely fashion.

Any death or liver transplant occurring from Randomization through the last day of study participation or through Study Day 91, must be reported to the Sponsor regardless of how much time has elapsed since the last exposure to investigational product treatment. The cause of death must be reported as an SAE, since death is an outcome and not an SAE. A death occurring after Study Day 91 that is not reasonably associated with investigational product treatment does not require completion of an SAE reporting form. However, both of these events should trigger completion of applicable VTL-308E eCRFs for the subject (see [Section 13](#)).

If progression of the underlying disease (i.e., the condition being treated with the investigational product) might be reasonably anticipated given the nature and severity of the underlying disease, then progression of the underlying disease per se will not constitute an adverse event. However, if the progression of the underlying disease meets the criterion for “serious” categorization of adverse events (e.g., the underlying disease results in premature death or prolonged hospitalization), then it should be reported as an SAE.

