13.1 VTL-308E JUSTIFICATION

VTL is conducting clinical trial VTL-308, in which subjects with AILD are treated with ELAD and standard of care, or with standard of care alone to assess the safety and efficacy of ELAD treatment.

A hypothetical risk exists that over an extended period of follow up there may be an increased incidence of tumor formation in subjects treated with ELAD. However, the underlying disease processes in subjects with alcoholic hepatitis also leads to an increased risk of tumor formation in the liver and elsewhere. Worldwide, hepatocellular cancer is the fifth most common cancer in men and eighth most common cancer in women, varying in accordance to prevalence of hepatitis B and C infections, and well over 80% of all primary liver cancers are caused by chronic hepatitis infections ([Bosch and Diaz 2004](#)).

The VTL-308 trial monitors subject safety up to 91 days after Randomization. To assess whether there is an increased risk of late tumor formation in subjects treated with ELAD, this registry protocol segment of VTL-308 extends the safety monitoring period to 5 years.

VTL-308E is designed to provide a long-term assessment of subject's outcome in relationship to tumor (in particular liver tumor), liver transplant, and overall mortality. The protocol includes both control and ELAD-treated subjects to assess the significance of any findings.

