5. The EQ-5D-5L Quality of Life questionnaire will be completed.

If the call recipient states the subject has expired:

If another person answers and states the subject is deceased, the investigative site's designated caller will ask the following:

6. When did the subject expire?
7. What was the cause of death?
8. Was an autopsy performed? If yes, where can a copy of the report be obtained?
9. Ask if signed approval can be obtained to access the subject's medical records that have the pertinent information (particularly if cancer was present) if the information is not in the medical record at the investigational site. If approval is given, the coordinator will send out the appropriate medical records release form for a legally appropriate family member to sign. A prepaid FedEx return envelope will be included.
10. Was the subject diagnosed with cancer after being in the VTL-308 study? If so:
 - a. What type of cancer was the subject diagnosed with?
 - b. What was the extent of the subject's metastatic disease (if applicable)? Again, ask in terms the caller can understand.
11. Had the subject had a liver transplant? If so, obtain the date of the transplant.

If the subject is deceased, it will be noted on the eCRF and no further follow-up will be initiated. Vital Therapies must be made aware of this to update the call reminder list. Call the office at [contact] and ask for any of the VTL-308 staff. Deaths, incidences of cancer, and liver transplants will not be reported as SAEs, but should be reported to Vital Therapies as soon as feasible.

Subject is not home/available:

If the subject is unavailable, the caller will find out when to call back to speak to the subject, or what a better phone number might be to reach the subject. A call-back number can be left for the subject.

A message can be left on a subject's voicemail or answering machine/service only if it gives no medical information or relationship to the reason of the call. For instance, "This call is for John Doe. Please call Jane at [contact] when you get this message." No reference to a clinic, doctor's office, etc. should be left unless the subject has previously stated this is allowed.

Subject not located or calls not returned:

If a subject is no longer at the number given, continues to be unavailable, or does not return messages for at least 3 attempts, the person listed as the contact person should be notified for information.

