4 STUDY POPULATION PARAMETERS

4.1 DISPOSITION

VTI-308 End of Study Disposition and VTL-308E Disposition at time of cut-off of all subjects will be presented in a table by treatment group for ITT population. These presentations will include the number of subjects who completed their Study Day 91 visit and the number who discontinued, as well as the reason for study discontinuation. The disposition for subjects who entered VTL-308E when the database locks will also be provided. Survival status at time of Day 91, Day 180, Day 365 and time of cut-off will be summarized using ITT populations. Additionally, subjects who received a liver transplant and/or were diagnosed with cancer will be summarized using the ITT population.

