5 DATABASES

Data will be collected in the Electronic Data Capture (EDC) system and other databases for the statistical analyses presented in this plan. The following table lists these databases and provides a description of the type of data being captured in each:

| Data Source | Primary Utility |
|-------------------------------|--|
| VTL-308 clinical database | Primary database for establishment of outcomes. Primary source of screening information, baseline characteristics, laboratory values, concomitant medications, adverse events (AEs), PEth lab results, ELAD Specialist data, and Home Health Care visit data. |
| VTL-308E interim data | Extension data documenting survival (at 6, 9, 12, and 24 months), transplant, incidence of cancer, and quality of life. Survival data earlier than 6 months may also be available for subjects who do not complete their Day 91 visit. Note: a snapshot of the VTL-308E database will be conducted at the time of the VTL-308 database lock to provide the updated information for the analysis of the primary endpoint of overall survival. |
| ELAD System performance files | Information recorded automatically by the ELAD System (Sorin S3/S5) documenting multiple system performance parameters during subject treatment. These data are stored in CSV format (one file per subject/cartridge set). |
| Manufacturing data | Files documenting ELAD cartridge performance and product release parameters such as albumin, transferrin, glucose consumption, and oxygen utilization, along with date of manufacture, and date of shipping. |

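### Late cancers, the stated reason for the 5-year extension, have no specified relatedness assessment or DSMB route; 9.4 and 13.4 conflict on product-associated late deaths; and the SAP counts cancers without person-time or an as-treated version

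*Protocol*

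**What the plan says.** - **Purpose.** Protocol 13.1 raises a hypothetical risk of tumours appearing long after ELAD and gives this as the reason that "this registry protocol segment of VTL-308 extends the safety monitoring period to 5 years". Both arms are followed so that findings can be compared.
- **Reporting in the extension.** Protocol 13.4: "Deaths, incidences of cancer, and liver transplants will not be reported as SAEs", "but should be reported to Vital Therapies as soon as feasible". No exception is made for events thought to be related to ELAD.
- **Reporting in the parent study.** Protocol 9.4: "SAEs should be reported from Randomization through the last day of study participation or through Study Day 91". Protocol 9.1 collects adverse events to Day 91, "or until subject discontinuation within this 91-day period". On later deaths, 9.4 adds: "A death occurring after Study Day 91 that is not reasonably associated with investigational product treatment does not require completion of an SAE reporting form".
- **What the call collects.** Under Protocol 13.4 a living subject is asked the type of cancer and whether it has spread. The date is asked for a transplant but not for a cancer. A records release is sought only in the part of the script for subjects who have died.
- **Analysis.** SAP 4.1, in the disposition section: "subjects who received a liver transplant and/or were diagnosed with cancer will be summarized using the ITT population". SAP 5 says that "a snapshot of the VTL-308E database will be conducted at the time of the VTL-308 database lock". By default, safety analyses use the Safety population (SAP 8), grouped by treatment actually received (SAP 3.4). The SAP plans no other analysis of cancers in the extension.

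**The concern.** The extension is set up to look for one named harm, but what happens once that harm is reported is left largely open.

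SAE status matters in this protocol. Section 9.9 lists serious adverse events among the data the DSMB reviews and does not name cancers. Expedited reporting under 9.4 depends on a judgement that a serious event is related. The trigger for suspending enrolment in Section 14 is an SAE or a system incident. A cancer recorded only in the registry reaches the sponsor, but no step is stated that takes it further.

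Timing makes this more than a formality. The extension calls at 6, 9 and 12 months begin while the parent trial is still randomising, so a tumour in an early subject could bear on subjects not yet treated.

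The analysis has a separate weakness. A count of subjects with cancer ignores how long each arm was at risk. The trial is designed on the expectation that one arm will live much longer, so the two counts would not be comparable.

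**Working it through.** **1. Reporting rules side by side**

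| Event after Day 91 | Protocol 9.4 | Protocol 13.4 | Result |
|---|---|---|---|
| Death not reasonably associated with product | SAE form waived | Not an SAE | Consistent |
| Death reasonably associated with product | Waiver does not apply | Not an SAE | Conflict |
| New cancer | Outside the SAE window | Not an SAE; tell the sponsor | Consistent, but no relatedness step, deadline or DSMB route |

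The reference in 9.4 to the last day of participation could be stretched to cover the extension. The wording in 9.1, which confines discontinuation to the 91-day period, points the other way.

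**2. Overlap with treatment**

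Protocol 7.1 assumes uniform accrual over at least 720 days. The first subject's 12-month call falls at about day 365, when (720 − 365)/720 = 49% of subjects are still to be randomised.

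**3. The plan's own survival figures**

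Protocol 7.1 gives a Control hazard of 0.004 and a hazard ratio (HR) of 0.4. Read per day, ELAD's hazard is 0.4 × 0.004 = 0.0016. The medians are ln2/0.004 = 173.3 and ln2/0.0016 = 433.2 days, within 3% of the stated 175 and 438. From SAP 1.3, 0.40^0.4 = 0.693 and 0.48^0.4 = 0.746, against the stated 69.5% and 74.5%. The inputs reproduce.

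**4. Person-time at lock**

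Assume exponential survival, no dropout, and potential follow-up uniform from 91 to 91 + 720 = 811 days. Mean days alive per subject for daily hazard λ are

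(1/λ) × [1 − (e^(−91λ) − e^(−811λ))/(720λ)]

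- Control, λ = 0.004: (0.6949 − 0.0390)/2.88 = 0.2277; (1 − 0.2277)/0.004 = 193 days.
- ELAD, λ = 0.0016: (0.8645 − 0.2732)/1.152 = 0.5133; (1 − 0.5133)/0.0016 = 304 days.
- Ratio: 304/193 = 1.58. With 75 per arm this is about 40 and 62 person-years.

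SAP-based hazards are −ln(S)/365.25, where S is one-year Control survival.

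| Assumption | Control (days) | ELAD (days) | Ratio |
|---|---|---|---|
| Protocol hazards, HR 0.4 | 193 | 304 | 1.58 |
| SAP, Control one-year survival 40%, HR 0.4 | 252 | 349 | 1.39 |
| SAP, Control one-year survival 48%, HR 0.4 | 279 | 366 | 1.31 |
| Protocol Control hazard, HR 0.7 | 193 | 238 | 1.23 |
| Protocol Control hazard, HR 1.0 | 193 | 193 | 1.00 |

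SAP 1.3 estimates lock at about 5 months after the last enrolment. Using 150 days in place of 91 moves the first ratio only to 333/205 = 1.62.

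**5. Likely number of cancers**

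The documents give no cancer rate. Assuming 0.5% to 5% per person-year, equal in both arms, and the protocol hazards, the expected counts at lock are about 0.2 to 1.9 in Control and 0.3 to 3.0 in ELAD. That is a crude ratio near 1.57 with no true difference in risk.

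**The case against.** Four points on the other side have weight.

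- **Events do reach the sponsor.** A reader who stops halfway through the sentence in 13.4 might infer that late cancers go unreported or cannot be acted on. The sentence continues with a duty to tell the sponsor. Subjects are also asked to notify the investigator of a cancer at any time, and cause of death and autopsy are sought. What is missing is a stated relatedness judgement, a deadline and an onward route.
- **A reader might infer that 13.4 contradicts 9.4 on cancers too.** It does not. A tumour at month 9 lies outside the 9.4 window, so the conflict is confined to product-associated deaths after Day 91.
- **The extension has its own protocol.** Protocol 13 refers to a separate VTL-308E document, which was not available for this review. It may contain the missing steps, so the point is about what the supplied documents specify.
- **The SAP table is modest and not the only view.** SAP 4.1 is descriptive, with no test. SAP 8 lists all CRF data and SAP 9 provides a narrative for every randomised subject, so individual cancers in the data would be visible. Consent under Protocol 10.2 already allows sponsor access to relevant medical records, although the call script does not direct sites to obtain them for living subjects.

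It is also tempting to apply the person-time argument at 5 years, where the imbalance would be larger. That does not bear on SAP 4.1, which uses a snapshot at lock. On a 720-day accrual no subject would then have more than about 811 days of follow-up, and this SAP contains no 5-year cancer analysis.

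Finally, under the design assumption unequal follow-up inflates ELAD's count; it does not hide harm. The concern about a hidden signal rests on the missing relatedness step and on the ITT grouping.

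**Conclusion.** The point holds in three limited parts.

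1. Protocol 9.4 and 13.4 give opposite instructions for a death after Day 91 that is reasonably associated with the product, and must be reconciled.
2. For late cancers the supplied documents specify no individual relatedness assessment, reporting deadline or DSMB route, and the call omits the diagnosis date. This is a gap, subject to what the VTL-308E protocol says.
3. The only planned cancer summary is by randomised arm, without person-time and without the as-treated grouping that the SAP uses for safety by default.

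The distortion from person-time is conditional: about 1.3 to 1.6 at lock if the assumed hazard ratio of 0.4 holds, 1.23 at 0.7, and none if survival is equal. These figures rest on exponential survival, 720-day uniform accrual and no dropout. The dilution from untreated ELAD-randomised subjects runs the other way; its size depends on how many there are, which the documents do not predict. With few cancers likely by lock, the practical weight lies more in parts 1 and 2 than in the table.

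**What to change.** 1. **Protocol 9.4 and 13.4.** Reconcile the two for product-associated deaths after Day 91. For any new cancer reported in VTL-308E, require an investigator relatedness assessment with a stated reporting deadline, and a route to the DSMB while it is constituted. If the VTL-308E protocol already provides this, cite the place.
2. **Follow-up call (Protocol 13.4).** Ask the date of cancer diagnosis, as is done for transplant, and obtain supporting records from living subjects who report a cancer. Without the date, the analysis in item 3 has no exact event time.
3. **SAP.** Report cancers per person-year, or as cumulative incidence with death as a competing event, for the ITT population and by treatment actually received. State the cut-off date and the person-time in each arm beside the counts.

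The cost is a few more forms for a small number of events, one added question, some records requests and one extra table. Sample size and the primary analysis are unaffected.

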13.5 MAINTAINING CONFIDENTIALITY

All efforts to maintain confidentiality of subject identification will be upheld. VTL will have the investigative site personnel call all subjects and maintain the contact information. Identifiable subject data will not be stored at VTL nor will it be made available to VTL.

A coding system will be in place using the coded patient identifiers used in VTL-308 (the subject number). Only the investigative site will have the corresponding subject names, phone numbers, addresses, and contact information in the event the subject cannot be reached. There will be no social security or medical record numbers stored.

A cover page with the subject identification coded will be completed at the site. This cover page will have the subject's full name, telephone number, and address. It will also have the name, telephone number, and address for their back-up contact should they be unreachable. This cover page, and any information contained within, will not leave the site or be made available to VTL or to the data management company.

Site staff must be aware of the importance of keeping subject data confidential. In accordance with ICH *Guideline for Good Clinical Practice*, confidentiality of records that could identify subjects must be protected, respecting the privacy and confidentiality rules in accordance with the applicable regulatory requirement(s).

Monitor(s), auditor(s), the IRB/EC, and the regulatory authority (ies) will be granted direct access to the subject's original medical records for verification of clinical trial procedures and/or data, without violating the confidentiality of the subject, to the extent permitted by the applicable laws and regulations and that, by signing a written informed consent form, the subject or the subject's legally acceptable representative is authorizing such access.

Records identifying the subject will be kept confidential and, to the extent permitted by the applicable laws and/or regulations, will not be made publicly available. If the results of the trial are published, the subject's identity will remain confidential.

